5.1.1 Inclusion Criteria

Philip Morris Products S.A.	Clinical Study Protocol	Confidential
ZRHR-PK-02-JP	Final 1.0 / 21 June 2013	Page 35 of 122

	Inclusion Criteria	Rationale	Screening	Day of Admission (Day -1)
5.	Subject smokes at least 10 commercially available CCs per day (no brand restrictions) with a maximum yield of 1 mg nicotine ISO/CC, as labeled on the cigarette package, for the last 4 weeks, based on self-reporting. Furthermore, the subject has been smoking for at least the last 3consecutive years. The smoking status will be verified based on a urinary cotinine test (cotinine ≥200 ng/mL).	Effect	X	X
6.	The subject does not plan to quit smoking in the next 3 months.	Safety	X	
7.	The subject is ready to accept interruptions of smoking for up to 4 days.	Safety	Х	Х
8.	The subject is ready to accept using both the THS 2.2 and NRT gum products.	Effect		Х

5.1.2 Exclusion Criteria

Subjects who meet any of the following exclusion criteria must not be enrolled into the study:

Exclusion Criteria	Rationale	Screening	Day of Admission (Day -1)
1. As per Investigator judgment, the subject cannot participate in the study for any reason (e.g., medical, psychiatric, and/or social reason).	Safety	Х	Х

Philip Morris Products S.A.

ZRHR-PK-02-JP

Clinical Study Protocol Final 1.0 / 21 June 2013 Confidential Page 36 of 122

	Exclusion Criteria	Rationale	Screening	Day of Admission (Day -1)
2.	A subject who is legally incompetent, physically or mentally incapable of giving consent (e.g., emergency situation, under guardianship, prisoners or subjects who are involuntarily incarcerated).	Administrative	Х	
3.	The subject has medical condition requiring smoking cessation, or clinically relevant diseases (including but not limited to gastrointestinal, renal, hepatic, neurological, haematological, endocrine, oncological, urological, immunological, pulmonary and cardiovascular disease or any other medical condition [including but not limited to clinically relevant abnormal laboratory parameters]) in the judgment of the Investigator.	Safety	X	X
4.	The subject has a body mass index (BMI) <18.5 or \ge 32.0 kg/m ² .	Safety	Х	Х
5.	As per Investigator judgment, the subject has medical conditions which require or will require in the course of the study, a medical intervention (e.g., start of treatment, surgery, hospitalization) which may interfere with the study participation and/or study results.	Effect	Х	Х

Philip Morris Products S.A.

ZRHR-PK-02-JP

Clinical Study Protocol Final 1.0 / 21 June 2013 Confidential Page 37 of 122

	Exclusion Criteria	Rationale	Screening	Day of Admission (Day -1)
6.	The subject has used nicotine-containing products other than commercially available CC (either tobacco-based products or nicotine-replacement therapy) as well as electronic cigarettes and similar devices, within 4 weeks prior to assessment.	Effect	X	X
7.	The subject has received medication (prescription or over-the-counter) within 14 days or within 5 half-lives of the drug prior to the Admission Day (Day -1; whichever is longer) that has an impact on CYP2A6 activity.	Effect		Х
8.	In case the subject received any medication (prescribed or over-the-counter) within 14 days prior to Screening or prior to the Admission Day (Day -1) it will be decided at the discretion of the Investigator if these can potentially interfere with the study objectives and subject's safety.	Effect	X	X
9.	The subject has a positive alcohol test and/or the subject has a history of alcohol abuse that could interfere with subject's participation in study.	Administrative	Х	Х
10.	The subject has a positive urine drug test.	Administrative	Х	Х
11.	Positive serology test for human immunodeficiency virus (HIV) 1/2, Hepatitis B or Hepatitis C.	Safety	Х	

Philip Morris Products S.A.	Clinical Study Protocol	Confidential
ZRHR-PK-02-JP	Final 1.0 / 21 June 2013	Page 38 of 122

Exclusion Criteria	Rationale	Screening	Day of Admission (Day -1)
12. Donation or receipt of whole blood or blood products within 3 months prior to Admission.	Safety	Х	Х
13. The subject is a current or former employee of the tobacco industry or of their first-degree relatives (parent, sibling, child).	Administrative	Х	
14. The subject is an employee of the investigational site or any other parties involved in the study or of their first-degree relatives (parent, sibling, child).	Administrative	Х	
15. The subject has participated in a clinical study within 3 months prior to the Screening Visit.	Safety	Х	
16. The subject has previously participated in the same study at a different time (i.e., each subject can be included in the study population only once).	Administrative	Х	
17. For women only:Subject is pregnant (does not have negative pregnancy tests at Screening and at Admission) or is breast feeding.	Safety	Х	Х
18. For women only:Subject does not agree to use an acceptable method of effective contraception.*	Safety	Х	Х

Philip Morris Products S.A.	Clinical Study Protocol	Confidential
ZRHR-PK-02-JP	Final 1.0 / 21 June 2013	Page 39 of 122

* Intrauterine device, intrauterine system, barrier methods of contraception (condoms, occlusive caps) with spermicidal foam/gel/film/suppository, hormonal contraception containing progesterone only, vasectomized partner(s) or true abstinence (periodic abstinence and withdrawal are not effective methods) from Screening until the end of the safety follow-up period. Hormonal contraception with estrogen containing products is NOT allowed in this study.

5.1.3 Removal of Subjects from the Study

Subjects will be informed that they are free to withdraw from the study at any time. Subjects should be questioned for the reason of premature withdrawal, although they are not obliged to disclose it. This needs to be fully documented in the Source Document and electronic Case Report Form (eCRF).

When a subject withdraws or is removed from the study, the whole examination procedure planned on Day 4 must be performed as soon as possible after the time of withdrawal unless the subject has withdrawn their informed consent to do so. After the time of withdrawal, the subject will enter into the 7-day period of safety follow-up. Subjects withdrawn or removed from the study cannot re-enter the study.

Subjects must be withdrawn from the study for any of the following reasons:

- Withdrawal of informed consent.
- Any AE or condition (including clinically relevant changes in a laboratory parameter), at the discretion of the Investigator.
- Positive pregnancy testing (any invasive procedures, including the drawing of blood MUST NOT be performed after diagnosis of pregnancy, see Section 8.5.1.
- The Sponsor or Principal Investigator terminates the study. If the Sponsor or the Principal Investigator decide to prematurely terminates the study, the head of the medical institution should be reported the fact and the reason in writing promptly.
- Withdrawal is considered to be in the best interest of the subject or the other subjects.

Subjects may be discontinued from the study for any of the following reasons:

- Lost to follow-up.
- Concomitant treatment with non-authorized medication as defined in the context of this study (in general, any concomitant medication should be discussed with the Contract Research Organization (CRO) Medical Monitor on an ongoing basis).

Philip Morris Products S.A.	Clinical Study Protocol	Confidential
ZRHR-PK-02-JP	Final 1.0 / 21 June 2013	Page 40 of 122

- If a subject uses any CC or nicotine/tobacco-containing product other than the product/regimen he/she is assigned to, it will be at the discretion of the Investigator to decide whether or not to withdraw the subject from the study.
- Non-compliance to the study procedures.

Subjects withdrawn prematurely after randomization will not be replaced and will not be allowed to re-enter the study. All subject withdrawals have to be documented properly in the source documentation and the eCRF.

5.1.4 Violation of Selection Criteria

Subjects who are eligible at Screening, but who do not meet the entry criteria at Admission Day (Day -1) will be considered a screening failure and will be replaced by other subjects.

Subjects who violate the entry criteria prior to enrolment, but who were considered eligible, will be immediately withdrawn from the study when the violation is detected. If subjects are not yet randomized, they can be replaced.

Confidential Page 41 of 122

6 INVESTIGATIONAL PRODUCTS AND REFERENCE POINT PRODUCT

6.1 Description

6.1.1 Investigational Products

THS 2.2:

THS 2.2 comprises the following components: Tobacco Stick, Holder, Charger, a Cleaning Tool, a mains power supply, and a USB cable:

Charger:	The function of the Charger (Model 4) is to recharge the Holder after use. It contains a battery with sufficient capacity to recharge the Holder approximately 20 times. It is a convenient size to carry
	around, and can itself be recharged from a mains power source.

- Tobacco Stick:The function of the Holder (Model 4.2) is to heat the Tobacco
Stick, delivering an aerosol to the user. The electrical heating is
powered from an internal battery which delivers power for about
6 minutes (allowing complete use of a single Tobacco Stick)
- THS Tobacco StickThe Tobacco Stick (product code C3) contains tobacco which,
when heated, generates an aerosol. It is custom-designed to be used
with the Holder.

The overall objective of the design is to provide an acceptable experience in which the HPHCs level in the aerosol is substantially reduced in comparison with CCs.

The THS 2.2 will be provided by the Sponsor.

Per cigarette/Tobacco Stick tar, nicotine, and carbon monoxide yields are normally determined by standardized test methods. The most widely used test method is ISO 4387. PMI has developed a modified version of this method, which improves the determination of tar in products with high water content, which is typical for heated tobacco products (PMI, 2012PMI, 2013a; PMI, 2013c). Another method is the more intensive smoking method developed by Health Canada (Health Canada, 1999).

Philip Morris Products S.A.	Clinical Study Protocol	Confidential
ZRHR-PK-02-JP	Final 1.0 / 21 June 2013	Page 42 of 122

Table 1 below lists the commonly reported measures:

Table 1Measured aerosol fractions for the THS Tobacco Sticks

Constituent (mg/THS Tobacco Stick)	ISO ¹	Health Canada Intense regime ²
Tar/NFDPM	4	10.3
Nicotine	0.5	1.32
Carbon monoxide	1	0.6

¹ International Organization for Standardization ISO machine-smoking regimen. The analytical method has been modified to avoid inaccuracies as a result of condensation from high water-content aerosols.

² Health Canada Intense machine-smoking regimen (55 mL puff volume, 2-second puff duration, 30-second inter-puff interval) (Health Canada, 1999)

Reference Product:

In the study sequences 1 and 2, the reference product to THS 2.2 is commercially available single brand CC with a maximum yield of 1 mg nicotine ISO per cigarette.

CC will not be provided by the Sponsor. All eligible subjects will be asked to purchase their own preferred single-brand CC prior to Admission. As randomization takes place on Day 0, every study subject needs to buy his/her anticipated amount of single-brand CC for a total of 2 days plus 2 extra packs.

6.1.2 Reference Point Product

Nicotine replacement therapy gum (Nicorette[®] 2 mg gum) is the reference point product to THS 2.2 for sequences 3 and 4. The NRT gum will be supplied by the site and reimbursed by the Sponsor.

6.1.3 **Packaging and Labeling**

At Admission on Day -1, all study subjects will provide the anticipated amount of CC in sealed packs to the site staff. The cigarette packs provided by the subject should not be opened and the cellophane wrapper should be intact.

Each pack of cigarettes provided by the subject will be labeled to identify which subject the cigarettes belong to (labels should be affixed by the study site trial collaborator to the cellophane wrapper of the lower part of the pack). Packs of CC will be labeled to identify necessary information to match the subject with his/her suppliers.

PMI RESEARCH & DEVELOPMENT

Philip Morris Products S.A.	Clinical Study Protocol	Confidential
ZRHR-PK-02-JP	Final 1.0 / 21 June 2013	Page 43 of 122

For the Tobacco Sticks, the packs and cartons will be pre-labeled with the necessary information including but not limited to product code. The labels will be written in Japanese (Appendix 4).

Philip Morris Products S.A.	Clinical Study Protocol	Confidential
ZRHR-PK-02-JP	Final 1.0 / 21 June 2013	Page 44 of 122

6.2 Use of Investigational and Reference Point Products

Subjects will never be requested or forced to smoke and will be free to stop smoking at any time during the study. Subjects caught using any nicotine/tobacco product which is different from the assigned product will be withdrawn from the study. During the Screening period, subjects will be allowed to smoke according to their smoking habits except during the procedures of the Screening Visit (see Section 6.2) at the discretion of the site.

6.2.1 Admission (Day -1)

Subject will be instructed not to smoke in the morning prior to Admission. Smoking *ad libitum* will be allowed throughout the day of admission except during the procedures until 11:00 PM. All subjects will be allowed to continue smoking *ad libitum* their preferred CC. All subjects (except women with a positive pregnancy test at Screening or Admission) will undergo a THS 2.2 test first (using up to 3 Tobacco Sticks) and subsequently NRT gum test at Day -1 prior to enrolment. Each subject will chew slowly the 2 mg NRT gum for $35\pm$ 5minutes while spacing each chew, leading to an administered dose of 1 mg nicotine/product use as per label similarly to the day of single use.

Following agreement that the THS 2.2 and NRT gum is acceptable, subjects will be enrolled and further randomized to 1 of 4 treatment sequences using an Interactive Web/Voice Response System.

6.2.2 Investigational Period (Day 0 to Day 3)

During the first washout, each subject will maintain nicotine abstinence from Day -1 at 11:00 PM to the time of single use of his/her allocated product at Day 1. At Day 1, after the single use of the product, subjects will maintain nicotine abstinence for the rest of the day. During the second washout on Day 2, subjects will maintain nicotine abstinence until the time of single use of subject's allocated product at Day 3. Subjects will not be allowed to smoke or use any other nicotine/tobacco-containing products other than the products/regimen they are allocated to.

Time point of first product use during study day (T_0) will be defined as start of the single product use at the single use days. The start time of the use of each product has to be documented on single use days (Day 1 and Day 3). The start of product use for THS 2.2 is defined as the time of the first puff. The start time for CC corresponds to the lighting of the CC, and the start time of the NRT gum is the time of the NRT gum intake. The 30 seconds it takes to pre-heat the Holder will not be taken into account. The subject must not take a puff of the Tobacco Stick during the pre-heating time.

Philip Morris Products S.A.	Clinical Study Protocol	Confidential
ZRHR-PK-02-JP	Final 1.0 / 21 June 2013	Page 45 of 122

For NRT gum, the start time and the stop time will be documented in appropriate log.

The start of the first product use can be different for each subject both days of product use; however, it must be in the window of 6:00 AM to 9:00 AM.

Single use of products (Day 1 and Day 3):

On Day 1 and Day 3, subjects will use the product they are randomized to only once in the morning between 6:00 AM to 9:00 AM, and will abstain from the product or other nicotine/tobacco-containing items for the rest of the day, i.e., subjects in the THS 2.2 arm will use one Tobacco Stick, subjects in the CC arm will smoke one CC, and subjects in the NRT gum arm will chew slowly the 2 mg NRT gum for 35±5minutes while spacing each chew (leading to an administered dose of 1 mg nicotine/product use as per label

	Sequence 1	Sequence 2	Sequence 3	Sequence 4
Day 1	THS 2.2	CC	THS 2.2	NRT gum
Day 3	CC	THS 2.2	NRT gum	THS 2.2

6.2.3 Day of Discharge/Time of Discharge

On the Day of Discharge (Day 4), smoking will be only allowed after all laboratory procedures and the spirometry have been performed. All examinations of the Day of Discharge will be conducted on Day 4 prior to the time of Discharge.

6.2.4 Safety Period

During the safety follow-up period, subjects are free to smoke according to their usual smoking habits.

6.2.5 Stopping Rules for Investigational Product

For safety purposes, smoking the THS 2.2 or the CC or the use of the NRT gum should be temporarily stopped in the event of any signs suggesting nicotine overexposure, e.g., gastrointestinal disturbance (nausea, vomiting, diarrhea, stomach, or abdominal pain), cold sweats, headache, dizziness and breathing problems, or any reasons at the discretion of the Investigator.

Philip Morris Products S.A.	Clinical Study Protocol	Confidential
ZRHR-PK-02-JP	Final 1.0 / 21 June 2013	Page 46 of 122

6.3 Method for Assigning Subjects to Study Arms

Randomization to product exposure sequence will be done through an Interactive Telephone and Web Response System.

Each sex and each of the smoking level (ISO nicotine levels ≤ 0.6 mg and >0.6 to ≤ 1 mg) will have a quota applied to ensure they represent at least 40% of the total study population allocated within each of the following analysis groups:

- Group 1: composed of sequences 1 and 2.
- Group 2: composed of sequences 3 and 4.

In particular, the maximum number of subjects having the same sex or nicotine level value will be limited to 26 in Group 1 and 10 in Group 2.

The randomization of the planned sample size of 62 subjects will be ensured by applying quota to the number of subjects per each sequence (22 subjects for sequences in Group-1, and 9 subjects for sequences in Group-2).

Subjects will be randomly assigned to one of the four product exposure sequences by means of a permuted-block schema. Block size and other randomization details will be available in the randomization plan.

The randomization plan will be generated by an independent statistician and none of the Sponsor staff, Investigators or study subjects will have access to the randomization schema prior to randomization.

6.4 Blinding

This is an open-label study; therefore the subjects and investigators will be unblinded to subject's sequence. However, there will be a limited degree of blinding in the data review and data analysis process. In particular, PMI and CRO personnel will be blinded to the randomized sequence as summarized in the following table:

Blinded Study Personnel	End of Blinding Period
PMI and CRO study statisticians	After the Statistical Analysis Plan (SAP) finalization or PMI blind database review ^(*) , whichever comes last.
PMI data manager	After the finalization of PMI blind database review. ^(*)

PMI RESEARCH & DEVELOPMENT

Philip Morris Products S.A.	Clinical Study Protocol	Confidential
ZRHR-PK-02-JP	Final 1.0 / 21 June 2013	Page 47 of 122
PMI safety and clinical scientist	After the finalization of PMI blind of be actively un-blinded before that the occurrence of any safety question, w	me point in case of the

(*) As part of the PMI Quality Control (QC) activity, data listings will be reviewed by PMI before database lock, with no access to the randomization sequence information

Any PMI and CRO personnel who are not listed in the above table will be unblinded by default.

6.5 Investigational Product Accountability and Compliance

6.5.1 Dispensing Investigational Product and Reference Point Products

From Day -1 until Day 4, the THS 2.2, NRT gum, and CC will be dispensed by the Investigators or dedicated study collaborator, as per study design. Each dispense of the product will be recorded in a log. The log should include subject number, date and start time of product use. The product will not be promoted for commercial distribution or test market.

6.5.2 Storage and Accountability

The THS 2.2, NRT gum and CC will be stored in a secured site storage place with access limited to the authorized personnel only. Full accountability of the distributed products will be ensured by designated collaborator. Subjects will return each butt of any used Tobacco Stick or CC immediately after use to the site study collaborator for accountability. They will also return each used NRT gum after use to the site study collaborator. This will be documented in appropriate log. On the time of discharge, unused CCs given to the site staff at Admission on Day -1 will be given back to the subjects.

6.5.3 Investigational Product Retention

Unused Tobacco Sticks and NRT gum will be destroyed if possible, or returned to the Sponsor upon study completion. The Tobacco Heating Devices will be returned to the Sponsor.

6.5.4 Compliance to Investigational Products

Compliance for all arms will be ensured by strict distribution of the products (product by product) and collection of used Tobacco Sticks, the CC butts and the NRT gum after use will be documented in appropriate logs.

Confidentiality statement: Data and information contained in this document are considered to constitute trade secrets and confidential commercial information, and the legal protections provided to such trade secrets and confidential information are hereby claimed under the provisions of applicable law. No part of this document may be publicly disclosed without the written consent of Philip Morris Products S.A.

Philip Morris Products S.A.	Clinical Study Protocol	Confidential
ZRHR-PK-02-JP	Final 1.0 / 21 June 2013	Page 48 of 122

In addition, for subjects using NRT gum, the compliance will be chemically verified using exhaled CO breath. The cut-off point for the CO breath test value to distinguish tobacco use vs. no tobacco use will be 10 ppm (Benowitz et al., 2002).

Furthermore, the CO breath test will be considered as one of the measures of compliance during the wash-out days in all subjects.

6.6 Restrictions

6.6.1 Smoking Restrictions

On Day 1 and Day 3, to avoid nicotine cross contamination, users of THS 2.2 and smokers of CC will use or smoke, as applicable, in dedicated separate rooms: one room for THS 2.2 and one room for CC. Every subject must use or smoke, as applicable alone with an interval between subjects allowing ventilation of the room. Subjects receiving NRT gum must not have access to these rooms.

In the morning prior admission, subjects will be instructed not to smoke. At admission, smoking is only allowed during the designated smoking times from 6:30 AM to 11:00 PM as detailed in the study design. Subjects will not have free access to their NRT gum, CC or THS 2.2, which will be dispensed by the site staff individually as described in Section 6.5.1.

Smoking is not allowed during study procedures except during blood sampling for nicotine PK on Day 1 and Day 3. Furthermore, smoking is not allowed on Day 4 until all laboratory tests and the spirometry have been conducted.

During the days of wash-out or single product use (for CC and THS 2.2 arms), no NRT gum or other products supportive to SA must be used or will be provided to the subjects.

6.6.2 Dietary Restrictions

A standard diet will be designed by a dietician for the whole confinement period. For each meal, the caloric and fat content should be controlled in order to avoid a "high-fat" diet. The FDA guidance on food-effect studies for bioequivalency testing identifies a "high-fat" diet as a diet which maintains approximately 50 percent of total caloric content of the meal and is high in calories (approximately 800 to 1000 calories) (FDA, 2002).

Subjects are not allowed to bring their own food or beverages to the investigational site. Meals will be served according to the schedules provided in Section 9. Additional light snack, fruits, and raw vegetables can be distributed to the subjects without restrictions at any time during confinement as long as they fulfill the above requirements described in this section. Consumption of water is allowed as desired. The same menu and meal schedule will be administered uniformly for all subjects in all study arms. Fasting state has to be observed

Confidentiality statement: Data and information contained in this document are considered to constitute trade secrets and confidential commercial information, and the legal protections provided to such trade secrets and confidential information are hereby claimed under the provisions of applicable law. No part of this document may be publicly disclosed without the written consent of Philip Morris Products S.A.

Philip Morris Products S.A.	Clinical Study Protocol	Confidential
ZRHR-PK-02-JP	Final 1.0 / 21 June 2013	Page 49 of 122

for at least 10 hours prior to blood draws for the safety laboratory at the Screening Visit, on Day -1, and Day 4.

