6.6.4 Others

From admission to discharge, practice of intensive exercise and physical work-out will be prohibited as it may impact nicotine absorption profile.

Philip Morris Products S.A.	Clinical Study Protocol	Confidential
ZRHR-PK-02-JP	Final 1.0 / 21 June 2013	Page 52 of 122

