9.3.2 Days of Single Use (Day 1 and Day 3)

On the days of single use (Day 1 and Day 3) the following assessments will be performed (Table 8):

Philip Morris Products S.A.	Clinical Study Protocol	Confidential
ZRHR-PK-02-JP	Final 1.0 / 21 June 2013	Page 79 of 122

onfidential

Table 8. Time Schedule – Day 1 and Day 3 Product Use

Time	Blood sample	Procedures	Additional information
Start of procedure			
		Optional: light snacks prior to first blood draw of the day	
		AE/SAE recording, concomitant medication	All day
		Craving questionnaire (QSU-brief)	For subjects on THS 2.2 or on CC: First sample within 15 min prior to T_0 , 9 assessments thereafter in relation to T_0 : 15 min, 30 min, 45 min, 60 min, 2 hr, 4 hrs, 6 hrs, 9 hrs, and 12 hrs after T_0 , with an allowed time window of +10 min each
			For subjects on NRT gum: First sample within 15 min prior to T_0 , 9 assessments thereafter in relation to T_0 : 20 min, 30 min, 45 min, 60 min, 2 hr, 4 hr, 6 hrs, 9 hrs, and 12 hrs after T_0 , with an allowed time window of +10 min each

PMI RESEARCH & DEVELOPMENT

Philip Morris Products S.A.	Clinical Study Pro	
ZRHR-PK-02-JP	Final 1.0 / 21 June	2013 Page 80 of 122
\checkmark	Plasma nicotine sample	For subjects on THS 2.2 or on CC: a total of 16 blood samples will be taken for a 24-hour profile (Day 1 and Day 3). The first blood sample will be taken within 15 min prior to T_0 and 15 samples thereafter in relation to T_0 : T_1 after 2 min +1 min, T_2 after 4 min +1 min, T_3 after 6 min +1 min, T_4 after 8 min +1 min, T_5 after 10 min +1 min, T_6 after 15 min +2 min, T_7 after 30 min +2 min, T_8 after 45 min +2 min, T_9 after 60 min +3 min, T_{10} after 2 hrs +5 min, T_{11} after 4 hrs +5 min, T_{12} after 6 hrs +5 min, T_{13} after 9 hrs +5 min, T_{14} after 12 hrs +5 min, and T_{15} after 24 hrs +5 min (this sample will be drawn during the day following product use, i.e., wash-out).

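### Food and drink on the two product-use days are not tied to T0, so a subject's two nicotine profiles can be taken in different fed states and drinking is allowed during the gum chew.

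*Protocol*

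**What the plan says.** Protocol Section 6.6.2 requires a dietician-designed standard diet with controlled calories and fat, bars subjects' own food, and states: "The same menu and meal schedule will be administered uniformly for all subjects in all study arms". The same section then says: "Additional light snack, fruits, and raw vegetables can be distributed to the subjects without restrictions at any time during confinement". A condition attached to this sentence holds such snacks to the fat and calorie limits; it restricts content, not timing. On water: "Consumption of water is allowed as desired". The only fasting rule in the section applies "for at least 10 hours prior to blood draws for the safety laboratory at the Screening Visit, on Day -1, and Day 4". Day 1 and Day 3, which produce the primary endpoints, have none.

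Table 8 (Section 9.3.2), the timetable for those two days, begins with "Optional: light snacks prior to first blood draw of the day" and gives breakfast a latest clock time of 10:00 AM with no interval from T0.

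On timing of use, Section 6.2.2 says: "The start of the first product use can be different for each subject both days of product use", within 6:00 to 9:00 AM. The gum instruction there covers the length and manner of chewing (35±5 minutes, slowly, spaced) and does not mention food or drink.

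The primary ANOVA (protocol Section 12.5.3, SAP Section 11.6.1) has terms for sequence, subject within sequence, period and product. The deviation categories and assessment windows listed in SAP Section 10.3 contain no item on food, drink or meal timing.

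**The concern.** In a crossover, anything that differs between a subject's two days other than the product enters the within-subject error. That error sets the width of the THS 2.2:CC interval, which is the success criterion, and the power of the THS 2.2 versus gum tests. As written, a subject can use one product after an overnight fast and the other soon after a snack or breakfast, and nothing in the model or the deviation review would pick this up.

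Gum raises a separate question. It is held in the mouth for about 35 minutes, during which water is expressly allowed and eating is not forbidden. Any nicotine exposure lost that way affects gum only. It travels with the product, so randomising the sequence does not remove it, and it raises the THS 2.2:gum ratio, the direction of the one-sided alternative.

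The protocol accepts that conditions of this kind matter. Section 6.6.2 cites food-effect guidance, and Section 6.6.4 says that intensive exercise "will be prohibited as it may impact nicotine absorption profile".

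**Working it through.** **Timing.** The largest T0 shift is 09:00 − 06:00 = 3 h. With T0 at 06:00, breakfast may come up to 4 h later. With T0 at 09:00, the 10:00 AM limit can be met only by eating before product use or within the first hour (10:00 − 09:00 = 60 min), while the dense early samples are being drawn. A uniform clock schedule does not equalise this. If breakfast were fixed at 09:30 (assumption), the gap from T0 would be 3.5 h for a 06:00 start and 0.5 h for a 09:00 start.

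**The plan's own figures first.** The inputs, from protocol Section 12.2 and SAP Section 8, are within-subject CV 36% (Cmax) and 21% (AUC), a ±20% margin with 90% probability, a gum AUC ratio of 1.28 with 90% power, and drop-out of at most 10%.

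- Within-subject log variance: σ² = ln(1 + CV²), giving 0.1219 for Cmax and 0.0432 for AUC. SD of a paired difference = √(2σ²).
- Probability of meeting the margin: P = χ²-CDF with df degrees of freedom, evaluated at df·(h√n / (t·SD))², where h = ln 1.2 = 0.182, t is the 97.5% t quantile and df = n − 2.
- For Cmax the smallest n with P ≥ 0.90 is 40 (P = 0.917), and 40 × 1.1 = 44, so the plan's 44 is reproduced. With all 44 evaluable, P = 0.976.
- For gum AUC, noncentral-t power at one-sided 0.025 with n = 18 and df = 16 is 0.917, so the plan's 18 is reproduced.

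**Adding a random fed state.** The documents give no food effect. Assume that being fed rather than fasted changes exposure by a factor d of 1.1 to 1.2, and that each day's state is a 50:50 draw. The added variance per profile is ½·½·(ln d)² = (ln d)²/4, that is 0.0023 (d = 1.1) or 0.0083 (d = 1.2).

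| Quantity | As planned | d = 1.1 | d = 1.2 |
|---|---|---|---|
| σ², AUC | 0.0432 | 0.0454 (+5%) | 0.0515 (+19%) |
| σ², Cmax | 0.1219 | 0.1241 (+2%) | 0.1302 (+7%) |
| P(margin met), AUC, n = 44 or 40 | about 1.00 | about 1.00 | about 1.00 |
| P(margin met), Cmax, n = 44 | 0.976 | 0.97 | 0.95 |
| P(margin met), Cmax, n = 40 | 0.917 | 0.90 | 0.86 |
| Power, gum AUC, n = 18, ratio 1.28 | 0.917 | 0.903 | 0.865 |
| Power, gum Cmax, n = 18, ratio 2.00 | >0.999 | >0.999 | >0.999 |

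AUC intervals become 2.6% to 9.2% wider (√1.053 to √1.193), but the expected AUC half-width with n = 44 goes only from 0.089 to 0.092-0.098, against a limit of 0.182.

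**Direction for gum.** If a share p of chews loses a fraction y of exposure, the geometric mean for gum is multiplied by (1 − y)^p, so the THS 2.2:gum ratio is multiplied by (1 − y)^(−p), which exceeds 1 for any loss. Neither p nor y is in the documents.

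**The case against.** The strongest reply is that the consequences are small and rest on assumptions that lean high.

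- A 50:50 fed state gives the largest variance a two-state model can have. The calculation applies the same effect to inhaled products and gum, although no document supports a food effect on inhaled nicotine. If only gum were affected, the added variance halves and gum AUC power is 91-89%.
- The planning CVs come from an earlier study whose diet rules are not given, so they may already contain some of this variation.
- Diet content and the meal clock are controlled, and randomised sequence makes any effect on THS 2.2:CC mainly noise, not bias.
- The Section 6.2.2 sentence on start times is ambiguous. It can mean that start times differ between subjects on both days, which fits the one-subject-at-a-time room use in Section 6.6.1. A 3 h shift within a subject is a permitted extreme, not a planned feature.
- Eating during the chew is inferred from silence. Gum subjects have seven blood draws and three questionnaires scheduled between 10 and 45 minutes, and site staff distribute the snacks. Only water is expressly allowed.

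All of this stands, and it limits the size of the point. It does not remove the gap. The uniform schedule fixes clock time, not time from T0, and an optional snack plus unrestricted extra snacks undo the uniformity just where it matters.

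A reader might go further and infer that the gum test's error rate is badly inflated. One can obtain about 33% instead of 2.5% at a true ratio of 1, but only by assuming that half of all chews lose 20% of exposure. With p of 20% or 50% and y of 10% or 20%, the other three combinations give 5% to 11%, and all these inputs are invented. The documents support the direction of the bias if exposure is lost, not that a loss occurs or how large it is.

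**Conclusion.** The point holds as a worthwhile, inexpensive improvement. On Day 1 and Day 3 the plan expressly allows food and drink without reference to T0, so a subject's two profiles can differ in fed state.

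For THS 2.2:CC the cost is avoidable within-subject noise. Under the assumed 10-20% effect, the AUC criterion is untouched and Cmax falls below the planned 90% only at the 20% end with 40 completers. These figures use ln 1.2 as the margin, the reading that reproduces 44. Reading ±20% as 0.20 on the log scale or as −ln 0.8 (0.223) is looser and leaves more room.

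For THS 2.2:gum the cost is about 2 to 5 percentage points of AUC power, plus a possible bias of unknown size in favour of the tested alternative.

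A reader might also infer that 44 and 18 are too few, or that the primary success criterion is in danger. The documents do not support either: both sample sizes are reproduced from the stated inputs, and no food effect is documented.

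**What to change.** Reconcile Section 6.6.2, Table 8 and Section 6.2.2 so that food and drink on Day 1 and Day 3 are specified relative to T0 and are the same on both days for each subject. The text should cover:

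- whether the snack before the first draw is given, and if so identically on both days;
- when breakfast falls relative to the first-hour samples;
- whether food and drink are allowed during product use, including the gum chew.

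In Section 6.2.2, state whether T0 may differ between a subject's two days, and schedule it at a similar clock time on both as far as the one-at-a-time room use in Section 6.6.1 permits. The intervals and the tolerance are for the sponsor to set. Cohort size is not given, so a very tight tolerance may not be workable.

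The cost is protocol wording, a tighter site timetable and a later breakfast for late starters. Subjects are confined and site-fed, and staff dispense the products, so no extra subjects or samples are needed.
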